18. SAFETY OUTCOMES

All outputs for safety outcomes will be based on the Safety Set. There will be no statistical comparisons between the treatment groups for safety data, unless otherwise specified. Subjects will be analyzed according to treatment received in the Double-Blind Treatment Period and Extension Treatment Period. Unless otherwise specified, the safety analyses will be conducted for Double-Blind Treatment period and Extension Treatment period, respectively, when its applicable.

18.1. ADVERSE EVENTS

Adverse Events (AEs) will be coded using MedDRA (version 25.1 or higher). Treatment-emergent adverse events (TEAEs) are defined as follows for Double-Blind Treatment period and Extension Treatment period, respectively:

- Double-Blind Treatment period: TEAE is defined as AEs that started or worsened in severity on or after the first dose of study treatment (etrasimod 1 mg, 2 mg or placebo) in Double-Blind Treatment period.
- Extension Treatment period: TEAE is defined as AEs that started or worsened in severity on or after the first dose of study treatment (etrasimod 1 mg or 2 mg) in Extension Treatment period.

See APPENDIX 2 for handling of partial dates for AEs for the purpose of assigning treatment-emergent flags. In the case where it is not possible to define an AE as treatment-emergent or not, the AE will be classified as treatment-emergent.

An overall summary of number of subjects within each of the categories described in the sub-section below, will be provided as specified in the templates. Listings will include TEAEs and Non-TEAEs.

18.2. ALL TEAEs

All TEAEs will be summarized by SOC and PT. This summary table and all other TEAE summaries by SOC and PT will be presented by descending frequency in the etrasimod pooled (1 mg and 2 mg) group. All AEs, regardless of treatment emergent status, will be included in an AE listing. Additionally, a listing of other AE details as collected on the CRF will be presented.

18.2.1. SEVERITY

Severity is classified as Grade 1: Mild, Grade 2: Moderate, Grade 3: Severe, Grade 4: Life-Threatening, Grade 5: Death Related to AE, using the Common Terminology Criteria for Adverse Events, version 5.0 (CTCAE v5.0).

All TEAEs will be summarized by SOC, PT, and maximum severity, with SOC and PT presented by descending frequency. If a subject reports a TEAE more than once within a SOC/PT, the AE with the worst-case severity will be used in this summary.

18.2.2. RELATIONSHIP TO STUDY TREATMENT

Relationship is classified as “not related”, “unlikely related”, “probably related”, or “related” by the Investigator.

All related TEAEs will be summarized by SOC and PT. A “related TEAE” for the purpose of this summaries is defined as a TEAE with relationship to study drug of “probably related” or “related”.

All TEAEs will be summarized by SOC, PT, and highest relationship (as reported on the eCRF, not grouped), with SOC and PT presented by descending frequency. If a subject reports a TEAE more than once within a SOC/PT, the AE with the worst-case relationship to study treatment will be used in this summary. TEAEs with a missing relationship to study treatment will be regarded as “Related” to study treatment for summary tabulation purpose only.

18.2.3. TEAEs LEADING TO DISCONTINUATION OF STUDY TREATMENT

TEAEs leading to permanent discontinuation of study treatment will be identified by action taken being recorded as “Drug withdrawal” on the Adverse events eCRF.

All TEAEs leading to discontinuation of study treatment will be summarized by SOC and PT. A listing of all TEAEs leading to discontinuation of study treatment will also be presented.

18.2.4. SERIOUS ADVERSE EVENTS

Serious adverse events (SAEs) are those events recorded as “Serious” on the Adverse Event eCRF.

All serious TEAEs will be summarized by SOC and PT. If the seriousness is missing, the AE will be considered as “Serious”. A serious TEAE listing will also be presented. All non-serious TEAEs will also be summarized by SOC and PT.

18.2.5. TEAEs LEADING TO DEATH

TEAEs leading to Death are those events which are recorded with an outcome as “Fatal” on the Adverse Events eCRF. All TEAEs leading to death will be listed.

18.2.6. TEAEs OF SPECIAL INTEREST

Categories of Targeted Medical Events (TMEs) and a list of preferred terms associated with these TME categories were developed based on the mechanism of action of etrasimod, prior experience with other agents acting via a similar mechanism, and disease-specific clinical judgment. In addition, where standard testing has been implemented to screen for potential AEs (eg, electrocardiograms, spirometry, serum transaminases, etc.), the relevant data will be reviewed to identify potential cases of AESI that investigators may not have identified and to provide quantitative data for AESIs. The proposed candidate terms will be reviewed to identify which events reflect AESI.

TEAEs of special interest will be summarized by category, subcategory, and PT by descending frequency by treatment group. Categories and subcategories of TEAEs of special interest are the following:

- Cardiovascular Events
 - Bradycardia
 - AV conduction delay
 - Hypertension
- Infections
 - Severe infections
 - Opportunistic infections (Narrow)
 - Herpes simplex and herpes zoster
- Macular Edema
- Pulmonary Disorders
 - Airflow obstruction (forced expiratory volume in 1 second [FEV₁], forced vital capacity [FVC])
 - Decrease gas exchange (diffusing capacity of the lungs for carbon monoxide [DLCO])
- Liver Injury
 - Liver transaminases elevation
 - Bilirubin elevation
 - Elevated BP
- Posterior reversible encephalopathy syndrome (PRES)
- Malignancies

For the TEAE of special interest, the Exposure-adjusted incidence rate (EAIR) will also be provided for the following group based on the subject in Safety Set in Double-Blinded Treatment Period

Group 1: Subjects who take etrasimod 2 mg anytime during the course of study. This includes the subjects who

- receive the etrasimod 2 mg in Double-Blind Treatment period and continue receiving Etrasimod 2 mg in Extension Treatment period, or
- receive the etrasimod 2 mg in Double-Blind Treatment period and discontinue early without entering Extension Treatment period, or
- receive the placebo in Double-Blind Treatment period and receive etrasimod 2 mg in Extension Treatment period

Group 2: Subjects who take etrasimod 1 mg anytime during the course of study. This includes the subjects who

- Subjects who take etrasimod 1 mg anytime during the course of study. This includes the subjects who
- receive the etrasimod 1 mg in Double-Blind Treatment period and continue receiving etrasimod 1 mg in Extension Treatment period, or
- receive the etrasimod 1 mg in Double-Blind Treatment period and discontinue early without entering Extension Treatment period, or
- receive the placebo in Double-Blind Treatment period and receive etrasimod 1 mg in Extension Treatment period

Group 3: Subjects who take placebo in Double-Blind Treatment period

The EAIR for a given TEAE of special interest is calculated as the number of subjects with the TEAE of special interest divided by the total exposure in subject-years. The 95% confidence interval (CI) of the EAIR will be provided along with EAIR. Some notes for the exposure and AE used in EAIR calculation are provided as follows

Group	Note for Exposure used in EAIR calculation	Note for TEAE of special interest used in EAIR calculation
1)	sum of either time (year) from first dose of etrasimod 2 mg to the onset of first such event for those who experienced the TEAE of interest, or time (year) from first dose of etrasimod 2 mg to last participation for those who did not experience the TEAE of special interest.	For a placebo subject who receive 2 mg in Extension Treatment period, only the AE that started or worsened in severity on or after the first dose of etrasimod 2 mg in Extension Treatment period will be included in the EAIR for the subject
2)	sum of either time (year) from first dose of etrasimod 1 mg to the onset of first such event for those who experienced the TEAE of interest, or time (year) from	For a placebo subject who receive 1 mg in Extension Treatment period, only the AE that started or worsened in severity on or

	first dose of etrasimod 1 mg to last participation for those who did not experience the TEAE of special interest.	after the first dose of etrasimod 1 mg in Extension Treatment period will be included in the EAIR for the subject
3)	sum of either time (year) from first dose of placebo to the onset of first such event for those who experienced the TEAE of interest during Double-Blind Treatment period, or time (year) from first dose of placebo to last participation for those who did not experience the TEAE of special interest. during Double-Blind Treatment period	For a placebo subject in Double Blind Treatment period, only the AE that started or worsened in severity on or after the first dose of placebo in Double Blind Treatment period will be included in the EAIR for the subject

18.2.7. OVERALL SUMMARY OF ADVERSE EVENTS

In addition to the summaries above, an overview of TEAEs will be summarized (not broken down by SOC or PT) by number and frequency of subjects and by number of AEs:

- Any TEAEs
 - Any related TEAEs*
- Any serious TEAEs
 - Any related serious TEAEs*
- TEAEs leading to death
- TEAEs leading to study drug discontinuation
 - Related TEAEs leading to study drug discontinuation
- TEAEs leading to study drug interruption
 - Related TEAEs leading to study drug interruption*
- TEAEs by maximum severity
 - Related TEAEs by maximum severity*
- TEAEs by relationship to study drug

* “Related TEAEs” refers to TEAEs related or probably related to study drug or are missing relationship.

18.3. DEATHS

Information collected about deaths (e.g., date of death, primary cause of death) will be presented in a data listing, as described in Section 18.2.5.

18.4. LABORATORY EVALUATIONS

No local laboratory assessments will be used in any summaries except for lipid panel and thyroid panel tests. No local laboratory assessments will be used to derive maximum/minimum/worst value. Local laboratory assessments will be listed.

18.4.1. SAFETY LABORATORY EVALUATIONS

Hematology, serum chemistry, and coagulation are analyzed and reported by central laboratory and sometimes by local laboratory. Results out of reference range are flagged by the performing laboratory (e.g., low, high). A full list of laboratory assessments to be included in the outputs is included in Table 3 of protocol amendment v3.0 (04Jan2023).

Presentations will use SI Units. Quantitative laboratory measurements reported as “< X” or “> X”, where X may be the lower limit of quantification (LLQ) or the upper limit of quantification (ULQ), respectively, will be converted to X for the purpose of quantitative summaries, but will be presented as recorded, i.e. as “< X” or “> X” in the listings. For urinalysis, only pH and specific gravity are considered as quantitative tests. If local and central laboratory assessments are available from the same day, central laboratory assessments will be used in the summary as per Section 6.4.

The following summaries will be provided for laboratory data:

- Value and change from Baseline by visit (for hematology, TBNK panel, serum chemistry, quantitative urinalysis [pH and specific gravity], and coagulation)
- Incidence of abnormal values according to laboratory reference ranges by visit
- Incidence of lymphocytes $< 0.2 \times 10^9/L$, $0.5 \times 10^9/L$, or neutrophils $< 0.5 \times 10^9/L$, $1 \times 10^9/L$ at end of treatment and anytime in the study
- Change and Percent Change from Baseline in Absolute Lymphocyte Count (ALC) at Weeks 16, 24, 32, and 52
- Shift from Baseline to end of treatment according to laboratory reference range (for quantitative measurements and categorical measurements)
- eDISH plots for the following laboratory assessments:
 - Maximum Alkaline Phosphatase vs. Same-Day Total Bilirubin
 - Maximum Alkaline Phosphatase vs. Same-Day Total Bilirubin Adjusted for Elevated Baseline
 - Maximum Alanine Aminotransferase vs. Same-Day Total Bilirubin
 - Maximum Alanine Aminotransferase vs. Same-Day Total Bilirubin Adjusted for Elevated Baseline
 - Maximum Aspartate Aminotransferase vs. Same-Day Total Bilirubin
 - Maximum Aspartate Aminotransferase vs. Same-Day Total Bilirubin Adjusted for Elevated

Baseline

If both central and local assessments of total bilirubin are available on the same day, the central result will take precedence over the local result in the eDISH plot. If the maximum AST/ALT/GGT assessment occurs at two different dates, the assessment with the higher accompanying Bilirubin value will be used. Two versions of the eDISH plots will be presented, with one showing values as multiples of upper limit of normal, and the other one showing values as multiples of upper limit of normal, or subject's baseline, whichever is higher.

Only laboratory tests completed by 50 or more subjects in the SAF will be presented in the summaries. All laboratory tests will be listed.

Subject's laboratory assessments at all timepoints will be listed in chronological order. Values outside of the laboratory reference range will be flagged. Values obtained from local laboratory will be flagged. Listing of lymphocytes and neutrophils over time in subjects ever with lymphocytes $<0.5 \times 10^9/L$ or neutrophils $< 1 \times 10^9/L$ will also be provided.

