11.9.1. Safety Endpoints

- Incidence and severity of AEs

- Incidence and severity of laboratory abnormalities, and change from baseline in laboratory values (to include hematology, serum chemistry, and coagulation)
- Incidence of clinically significant vital sign abnormalities and changes from baseline

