APPENDIX 8: GRADING OF CLINICAL AND LABORATORY ADVERSE EVENTS

All clinical and clinically significant laboratory abnormalities will be graded according to the Common Terminology Criteria for Adverse Events (CTCAE) Scale for Severity of Adverse Events and Laboratory Abnormalities.

Examples of CTCAE terms and grading are provided for clinical adverse events in [Table 10](#) and for laboratory abnormalities in [Table 11](#).

Table 10: Example of CTCAE Terms and Grading for Clinical Adverse Events

Respiratory, thoracic and mediastinal disorders					
CTCAE Term	Grade 1	Grade 2	Grade 3	Grade 4	Grade 5
Cough	Mild symptoms; nonprescription intervention indicated	Moderate symptoms; medical intervention indicated; limiting instrumental ADL	Severe symptoms; limiting self-care ADL	–	–
Definition: A disorder characterized by sudden, often repetitive, spasmodic contraction of the thoracic cavity, resulting in violent release of air from the lungs and usually accompanied by a distinctive sound.					
Dyspnea	Shortness of breath with moderate exertion	Shortness of breath with minimal exertion; limiting instrumental ADL	Shortness of breath at rest; limiting self-care ADL	Life-threatening consequences; urgent intervention indicated	Death
Definition: A disorder characterized by an uncomfortable sensation of difficulty breathing.					
Wheezing	Detectable airway noise with minimal symptoms	Moderate symptoms; medical intervention indicated; limiting instrumental ADL	Severe respiratory symptoms limiting self-care ADL; oxygen therapy or hospitalization indicated	Life-threatening consequences; urgent intervention indicated	Death
Definition: A disorder characterized by a high-pitched, whistling sound during breathing. It results from the narrowing or obstruction of the respiratory airways.					
Dizziness	Mild unsteadiness or sensation of movement	Moderate unsteadiness or sensation of movement; limiting instrumental ADL	Severe unsteadiness or sensation of movement; limiting self-care ADL	–	–
Definition: A disorder characterized by a disturbing sensation of lightheadedness, unsteadiness, giddiness, spinning or rocking.					

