6.3. RETESTS, UNSCHEDULED VISITS, AND EARLY TERMINATION DATA

For by-visit analyses and summaries, efficacy, safety, health-related quality of life, and CCI (including scheduled, retests, unscheduled, and early termination) will be assigned to visits after the application of the windowing conventions described in Section 6.4. All measurements will be considered in summaries of abnormalities or worst-case values post-Baseline.

The visit windowing will be applied before missing data are imputed.

Listings will include scheduled, unscheduled, retest, and early discontinuation data.

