If one or more results for a variable are assigned to the same analysis visit, the result with the date closest to the protocol scheduled day will be used in the analysis. If two measurements in the same analysis visit window are equidistant from the protocol scheduled study day, the earlier measurement will be used in the analysis. If multiple assessments are available on the same day, then the average of the assessment will be used in the analysis, except for laboratory and ECG data where the assessment at the earliest time of the same day will be used. If both central and local assessments of the same lab test are available on the same day, the central result will take precedence over the local result. If both central and local assessments of the same ECG test are available on the same day, the assessment of clinical significance by local reader will take precedence over the determination by a central reader.

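### Severity of laboratory abnormalities is a named safety endpoint, but from laboratory values the SAP shows it for only a few tests and plans no baseline-to-worst shift

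*SAP*

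**What the plan says.** Protocol 11.9.1 lists as a safety endpoint "Incidence and severity of laboratory abnormalities, and change from baseline in laboratory values", covering hematology, serum chemistry and coagulation. It stands beside a separate endpoint for the incidence and severity of adverse events.

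SAP 18.4.1 plans these laboratory outputs:

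- values and change from baseline by visit;
- "Incidence of abnormal values according to laboratory reference ranges by visit";
- lymphocyte and neutrophil cut-off counts, at end of treatment and at any time;
- change in absolute lymphocyte count at selected weeks;
- "Shift from Baseline to end of treatment according to laboratory reference range";
- eDISH plots of maximum ALP, ALT and AST against bilirubin on the same day, with versions adjusted for an elevated baseline.

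Three data rules also apply. SAP 6.3 states "All measurements will be considered in summaries of abnormalities or worst-case values post-Baseline". SAP 18.4 states "No local laboratory assessments will be used to derive maximum/minimum/worst value". SAP 6.4 states that when several results fall in one visit window "the result with the date closest to the protocol scheduled day will be used in the analysis".

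Outside the laboratory tables, Protocol Appendix 8 states "All clinical and clinically significant laboratory abnormalities will be graded according to the Common Terminology Criteria for Adverse Events", and SAP 18.2.1 tabulates treatment-emergent adverse events by maximum severity. SAP 18.2.6 adds that data from standard tests, including serum transaminases, will be "reviewed to identify potential cases of AESI that investigators may not have identified".

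**The concern.** A reference-range count gives a value just below the limit the same weight as one far below it. A shift to end of treatment loses anything that has resolved by then. Between them, these two outputs carry most of the laboratory panel, and neither expresses severity.

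Other safety domains are treated more fully. ECG interpretation has a shift to the worst post-baseline case (SAP 18.5). ECG, vital signs and pulmonary function each have markedly abnormal criteria (SAP 18.5.1, 18.6.2, 18.8.2). The laboratory section has no general equivalent.

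What is at stake is the safety half of dose selection, a primary objective (SAP 2.1). The natural question is how many subjects per dose reached a moderate or severe abnormality at any time. For most tests the planned laboratory tables do not answer it.

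**Working it through.** No sample size or error rate is involved, and the plan gives no figure to reproduce. The check is a count, followed by a small illustration.

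**1. Tests in scope.** Protocol Table 3, the three panels named in the endpoint, visible entries only:

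- CBC 8 + differential 5 = 13 hematology
- chemistry 14
- coagulation 2
- total 13 + 14 + 2 = 29

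**2. Tests with severity shown from values (SAP 18.4.1).** Lymphocytes and neutrophils (2), and maximum ALT, AST and ALP (3), make 5. Crediting total bilirubin, which is plotted only on the same day, makes 6. SAP 18.4.1 does not say whether the plots are split by arm; they are counted here in its favor.

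- 29 − 6 = 23, or 79%
- without bilirubin, 29 − 5 = 24, or 83%
- tests with a shift to the worst post-baseline value: 0 of 29

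**3. How many of the 23 could be graded.** Protocol Tables 10 and 11 show value-based grades for hemoglobin, platelets, ALT and AST. Two of these, hemoglobin and platelets, are among the 23. The other 21 must be checked in CTCAE v5.0. If the three red-cell indices (MCH, MCHC, MCV) are assumed not gradable, the ceiling is 23 − 3 = 20. The fix would therefore add graded output for 2 to 20 of these tests.

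**4. Samples that feed the shift.** Laboratory samples are scheduled at Weeks 4, 8, 16 and 24, and at Weeks 28, 32, 46 and 52 (Protocol Tables 7 and 8). With the shift produced for each period, a completer contributes 1 of 4 scheduled post-baseline samples to it. The other 3 of 4 (75%) enter only the by-visit tables.

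**5. Liver plots.** The eDISH plots pair the peak enzyme with bilirubin from the same day. Protocol Appendix 12 says transaminase rises mostly precede bilirubin rises by days or weeks, so a later bilirubin rise can fall outside the plotted pair.

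**6. Illustration, with assumed data.** Planned arms under 3:3:2 of 96 are 36, 36 and 24. Suppose k = 1, 2 or 3 of 36 subjects on 2 mg fall from 135 to 95 g/L hemoglobin at Week 8 and are back in range at Week 24. On Protocol Table 10, 95 g/L is Grade 2 (below 100 to 80 g/L).

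| Output | What it shows |
|---|---|
| End-of-treatment shift | 0 subjects |
| By-visit incidence, Week 8 | k more low subjects, mixed with slight cases |
| Week 8 arm mean, 40k/36 | lower by 1.1, 2.2 or 3.3 g/L |
| By-visit minimum | 95 if that result is the one selected for the window, but not in how many subjects |
| Adverse event table | 0 to k, depending on what is recorded |
| Worst-grade table (not planned) | 2.8%, 5.6% or 8.3% |

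Exact 95% intervals for the last row are 0.1% to 14.5%, 0.7% to 18.7% and 1.8% to 22.5%. Against 0 of 24 on placebo, Fisher's two-sided p is 1.00, 0.51 and 0.27. The added table describes; it does not test.

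**The case against.** The strongest reply is that the endpoint does have a planned by-arm output. Protocol 10.6.4 treats clinically significant laboratory abnormalities as adverse events and requires investigators to review each report and record relevant changes. These are graded by CTCAE and tabulated by maximum severity. Protocol 11.9.1 does not say that severity must come from laboratory values. Site staff are blinded on treatment only to WBC, its differential and the TBNK panel (Protocol 6.5), so investigators see 19 of the 23 tests. The hemoglobin fall above would be seen, and the zero end of its adverse event range is an assumption.

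Much of this stands. A reader might infer that severity goes unreported for 23 of 29 tests; the documents do not support that, because the adverse event tables and the special-interest review remain. A reader might also infer that the SAP departs from the protocol's laboratory analysis plan. Protocol 11.9.4 asks only for by-visit descriptives, range flags, shifts and changes, and the SAP supplies them. Nor do the worst-value rules in SAP 6.3 and 18.4 prove that a table was dropped, since they also serve the planned incidence counts and eDISH maxima. The SAP's emphasis on lymphocytes, neutrophils and liver tests follows the known risks.

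What does not stand is that this route closes the gap. It depends on investigator judgement, and the special-interest review states no cut-offs. For WBC, eosinophils, monocytes and basophils it is narrower still: the stated independent-monitor triggers (Protocol 10.6.7.2) are lymphocytes below 0.2, neutrophils below 1.0 and WBC above 20 × 10⁹/L, although values may be released when medically necessary. Listings of every value, flagged against range, are not a by-arm summary.

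**Conclusion.** The point holds in a limited form. The stated endpoint is only partly reported from the laboratory data: severity is visible from values for 5 or 6 of 29 tests, and no test has a baseline-to-worst shift. For the rest, a by-arm severity count depends on adverse event recording or the special-interest review.

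The figure of 23 describes the plan's coverage. It should not be read as the number of graded tables to be gained, which is 2 to 20 and is settled only by checking CTCAE v5.0. No efficacy result, sample size or error rate is affected.

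The conclusion rests on the SAP text and the visible part of Protocol Table 3. The table shells are a separate file and may already contain such outputs. This is a cheap improvement that could be made, not a necessary correction.

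**What to change.** In SAP 18.4.1 add, by treatment group and period:

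- (a) Incidence of the worst post-baseline CTCAE v5.0 grade, using value-based grades only, and a shift from baseline to worst post-baseline grade, for the gradable Protocol Table 3 tests. These are at least hemoglobin, platelets, ALT and AST, with the others to be confirmed against CTCAE v5.0. Use all scheduled and unscheduled central results, in line with SAP 6.3 and 18.4. Clinical grades, such as Grade 4 anemia in Protocol Table 10, stay with adverse event reporting.
- (b) Descriptive any-time counts of ALT or AST above 3, 5 and 8 × ULN, and of total bilirubin above 2 × ULN, to accompany the eDISH plots. Label them as screening counts. They are not the discontinuation criteria of Protocol 10.6.7.1, which require more than 2 weeks' duration at 5 × ULN, and accompanying bilirubin, INR or clinical findings at 3 × ULN.

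Keep the end-of-treatment shift. The cost is SAP wording and a few more standard tables from data already collected.
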